2. SYNOPSIS

Name of Sponsor/Company: Baylor Scott and White Research Institute	
Name of Investigational Products: Hydroxychloroquine 200 mg tablets	
Title of Study: A PROSPECTIVE CLINICAL STUDY OF HYDROXYCHLOROQUINE IN THE PREVENTION OF SARS-COV-2 (COVID-19) INFECTION IN HEALTH CARE WORKERS AFTER HIGH-RISK EXPOSURES	
Study center(s): Single center	
Studied period: 4 months Estimated date first subject enrolled: March 2020 Estimated date last subject completed: July 2020	Phase of development: 2
Objectives: For Healthcare workers with 
 One day or more of exposure to suspected and/or positive COVID-19 patients, including but not limited to those working in the Emergency Department or Intensive Care Unit. OR Unprotected exposure to a known positive COVID-19 patient within 72 hours of screening. Primary: 
 To assess the efficacy of hydroxychloroquine 400 mg (two 200 mg tablets) twice a day on day 1 followed by two 200 mg tablets once a week for a total of 7 weeks in the prevention of COVID-19 infection Secondary: 
 To compare the rate of COVID-19 positive conversion among emergency department workers versus intensive care unit workers 	
Endpoints: Primary Efficacy Endpoint: Rate of COVID-19 positive conversion on weekly nasopharyngeal (NP) sampling Secondary Efficacy Endpoint: Time-to-first clinical event consisting of a persistent change for any of the following: 
 One positive NP sample Common clinical symptoms of COVID-19 infection including fever, cough, and shortness of breath Less common signs and symptoms of COVID-19 infection including headache, muscle pain, abdominal pain, sputum production, and sore throat Exploratory Efficacy Endpoint: Time-to-first clinical worsening event consisting of any of the following: 
 Hospitalization for COVID-19 infection Intensive care unit admission for COVID-19 infection All cause death 	

Safety:

Participants will be closely monitored for any occurrence of adverse events or serious adverse events during the trial. Weekly in-person visits will be scheduled to capture the frequency, intensity, and relationship to study drug of (serious) adverse events. Body temperature will also be collected in all follow-up visits.

Methodology:

This prospective open label trial will study the safety, tolerability, and efficacy of hydroxychloroquine 400 mg po in qualified health care workers.

Qualified individuals will be prescribed oral hydroxychloroquine 400 mg twice a day (two 200 mg tablets twice a day) on day 1 followed by two 200 mg tablets once a week for a total of 7 weeks. Dose de-escalation is permitted during the study if indicated clinically. Please refer to [Section 7.3.1](#) for additional details on dose escalation and dose de-escalation.

All study individuals will follow the same visit and assessment schedule. Following study recruitment, participants will be scheduled to be assessed in person during treatment at days 7, 14, 21, 28, 35, 42 and 49.

Healthcare workers who are qualified for the trial but decline participation in receiving the treatment will form the control group and will be offered an observational registry where the same NP COVID-19 sampling schedule and other assessments will be followed with the exception of blood testing. The clinical outcomes will be captured in the same manner and with the same definitions as the clinical arm.

Number of Subjects (planned):

360 individuals will be enrolled into the study with half enrolling in the active treatment study and the other half, those who refuse to get the study treatment, will be entering an observational registry considered as the control group.

Main criteria for inclusion:

1. Adult male and female healthcare workers ≥ 18 to ≤ 75 years of age upon study consent
2. Healthcare workers with
 - One day or more of exposure to suspected and/or positive COVID-19 patients, including but not limited to those working in the Emergency Department or Intensive Care Unit.OR
 - Unprotected exposure to a known positive COVID-19 patient within 72 hours of screening.
3. Afebrile with no constitutional symptoms
4. Willing and able to comply with scheduled visits, treatment plan, and other study procedures
5. Evidence of a personally signed and dated informed consent document indicating that the subject (or a legally acceptable representative) has been informed of all pertinent aspects of the study prior to initiation of any subject-mandated procedures

Major exclusion criteria:

1. Participation in other investigational clinical trials for the treatment or prevention of SARS-COV-2 infection within 30days
2. Unwilling to practice acceptable methods of birth control (both males who have partners of childbearing potential and females of childbearing potential) during Screening, while taking study drug, and for at least 30 days after the last dose of study drug is ingested

Note: the following criteria follow standard clinical practice for FDA approved indications of this medication

3. Having a prior history of blood disorders such as aplastic anemia, agranulocytosis, leukopenia, or thrombocytopenia
4. Having a prior history of glucose-6-phosphate dehydrogenase (G-6-PD) deficiency
5. Having dermatitis, psoriasis or porphyria
6. Taking Digoxin, Mefloquine, methotrexate, cyclosporine, praziquantel, antacids and kaolin, cimetidine, ampicillin, Insulin or antidiabetic drugs, arrhythmogenic drugs, antiepileptic drugs, loop, thiazide, and related diuretics, laxatives and enemas, amphotericin B, high dose corticosteroids, and proton pump inhibitors, neostigmine, praziquantel, Pyridostigmine, tamoxifen citrate
7. Allergies: 4-Aminoquinolines
8. Pre-existing retinopathy of the eye
9. Has a chronic liver disease or cirrhosis, including hepatitis B and/or untreated hepatitis
10. Untreated or uncontrolled active bacterial, fungal infection
11. Known or suspected active drug or alcohol abuse, per investigator judgment
12. Women who are pregnant or breastfeeding
13. Known hypersensitivity to any component of the study drug
14. A known history of prolonged QT syndrome or history of additional risk factors for torsades de pointe (e.g., heart failure, requires a lab test , family history of Long QT Syndrome), or the use of concomitant medications that prolong the QT/QTc interval

Investigational product, dosage and mode of administration:

Oral hydroxychloroquine 400 mg twice a day (two 200 mg tabs twice a day) on day 1 followed by two 200 mg tablets once a week for a total of 7 weeks.

Duration of treatment:

Study drug will be administered for 7 weeks.

Criteria for evaluation:

Efficacy: Rate of COVID-19 positive conversion on weekly nasopharyngeal (NP) sampling

Safety: Body temperature measurements, adverse events, and serious adverse events.

Statistical methods:

Sample size: A total sample of 360 individuals (180 in each arm) would provide at least 80% power to detect a relative risk reduction of 40% in the rate of positive NP samples when the anticipated rate of positive conversion among those taking hydroxychloroquine is approximately 30%.

The power calculation, which was based on Pearson Chi Square test, assumes the following:

- One-sided Type I error rate of 0.05
- Anticipated positive NP samples rate of 30% in the clinical arm
- A 40% lower risk of a positive NP sample comparing the hydroxychloroquine group vs the controls
- Loss to follow-up rate of 15%

Primary analysis of efficacy:

The proportion of individuals who tested positive at least once during the study period will be compared between the clinical and the control arms. In addition, the potential effect of hydroxychloroquine on COVID-19 free survival time will also be explored by utilizing appropriate statistical methods. An intent-to-treat approach will be used throughout the analysis with the control group as the referent. A p-value < 0.05 will be considered statistically significant and a risk reduction of 5% will be considered as of smallest clinical importance.

Study Rationale

It is clear that close interaction of health care workers with patients put them at higher risk of getting exposed to infectious diseases. Failing to provide a safe environment for health care workers could cripple the medical system especially during an Epidemic outbreak like COVID-19. It is imperative to make sure that doctors and nurses do not get sick in high numbers; not only because that will contribute to spreading the virus among vulnerable patients but also due to their subsequent role in reducing the number of responding personnel. As a result, it is of utmost importance to provide effective prophylaxis to healthcare workers who are exposed to COVID-19.

Schema for Study of Prophylactic Therapies for COVID-19 Exposure

The trial design is initially for a 7 week treatment period which can be divided into 7 bins of time to allow a flexible design. Given the fluid nature of information flow in this pandemic that for example, new information comes forward clearly showing that 6 days is a sufficient period of time for proven prophylaxis, this trial design can be altered. Conversely if each subsequent qualifying exposure calls for another 6-day bin of time, the protocol can flex to the maximum 7 week period as stated for resource planning.

Once subject's eligibility is approved they may choose to either receive hydroxychloroquine or enter the observational registry. In both cases subjects will be tested for COVID-19 positive conversions on weekly nasopharyngeal (NP) sampling. The swab samples will be collected by trained personnel. Nasopharyngeal swab will be collected in a VCM medium tube or equivalent (UTM) or E-swabs/Amies medium (minitip-NP swab) or M4, M4RT, M5 and M6 transport media. The Roche Cobas test will be utilized for detecting nucleic acids from SARS-CoV-2 in nasopharyngeal swab samples collected from study participants.

The safety of the study participants will be ensured by closely monitoring the (serious) adverse events occurring during the trial. In addition, we will comply with the standard of care for regular prescribing of hydroxychloroquine which does not require a routine assessment of subject's health status especially for short-term use. However, since the package insert for hydroxychloroquine cautions on using antimalarial

compounds for individuals with hepatic disease, alcoholism, G-6-PD and severe blood disorder we will not include individuals having those diseases in our study.

Subjects who choose to enter the clinical arm of the study will receive hydroxychloroquine for a total of 7 weeks. The study drug supply will be maintained either through Baylor Scott & White pharmacies or directly from a manufacturer.

The logistics of drug dispensing will be specified based on the availability of drug supplies and also the mechanism through which the drug would be accessed. If there is enough supply of hydroxychloroquine we will dispense the drug as feasible in advance for future visits, otherwise a weekly supply would be provided to participants at each visit.

At the end of the study, after the last subject visit is completed. All collected data will be analyzed with the study population being those who either received hydroxychloroquine or entered the observational registry.

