7.5. Schedule of Assessments

[Table 3](#) lists the overall schedule of assessments for the study.

Table 3: Schedule of Assessments

Assessment	Study Day (Day)	Screen A ^a	Day 1 ^b	Day 7 Day 7±3	Day 14 Day 14±3	Day 21 Day 21±3	Day 28 Day 28±3	Day 35 Day 35±3	Day 42 Day 42±3	Day 49 ^j Day 49±3 (End of study visit)
Informed consent		X								
Inclusion/ exclusion		X	X ^c							
Self-reported Pregnancy Status ^d		X	X	X	X	X	X	X	X	X
Demographics and baseline disease characteristics		X								
Prior and Concomitant medications		X	X	X	X	X	X	X	X	X
Current background medications		X	X	X	X	X	X	X	X	X
Medical history		X								
Self-reported Height		X								
Self-reported Weight		X								
Body temperature		X	X	X	X	X	X	X	X	X
Study drug administration			X	X	X	X	X	X	X	
Dispense study drug ^e			X	X	X	X	X	X	X	
Collect study drug ^f				X	X	X	X	X	X	X
nasopharyngeal (NP) sampling			X	X	X	X	X	X	X	X
Adverse event collection			X ^g	X	X	X	X	X	X	X
Visual analogue scale (VAS) for cough severity		X	X	X	X	X	X	X	X	X
Exposure assessment		X	X	X	X	X	X	X	X	X
Virus serology ^h		X			X		X		X ⁱ	

^a Total Screening period should not exceed 30 days. Screening and Day 1 can be completed in the same visit.

^b Day 1 is the day of administration of the first dose. **On Day 1, all procedures should be performed before study drug administration.**

^c Screening eligibility procedures do not need to be repeated on Day 1; however, a review of any changes in eligibility criteria should be evaluated prior to Day 1 procedures

^d Female participants will be asked with respect to their pregnancy as a verbal check

^e Depending on the availability of the drug supply, the schedule of drug dispensing might change

^f If the schedule for drug dispensing changes, the arrangements for drug collection will change accordingly

^g AE assessments on Day 1 should be performed following study drug administration

^h Only applicable to those who choose to participate in the optional viral serology study

ⁱ Individuals who terminate from the study prior to the Day 49 study visit should return to the clinic as soon as possible for early termination assessments (*i.e.*, Day 49 Day Prior and end-of-treatment visits). Participants should complete the end-of-treatment procedures, including assessments, prior to any adjustments being made to their treatment regimen.

^j If final serology draw not collected at Day 42, it can be collected at day 49

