8. SELECTION AND WITHDRAWAL OF SUBJECTS

8.1. Subject Inclusion Criteria

1. Adult male and female healthcare workers ≥ 18 to ≤ 75 years of age upon study consent
 2. Healthcare workers with
 - One day or more of exposure to suspect and/or positive COVID-19 patients, including but not limited to those working in the Emergency Department or Intensive Care Unit.
- OR
- Unprotected exposure to a known positive COVID-19 patient within 72 hours of screening.
3. Afebrile with no constitutional symptoms
 4. Willing and able to comply with scheduled visits, treatment plan, and other study procedures
 5. Evidence of a personally signed and dated informed consent document indicating that the subject (or a legally acceptable representative) has been informed of all pertinent aspects of the study prior to initiation of any subject-mandated procedures

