9.8.17. Optional Viral Serology Study

Infection with SARS-COVID-2 may range from asymptomatic to disease requiring hospitalization. Given a high number of asymptomatic or minimally symptomatic infections, it is possible that a proportion of the population could have been exposed and recovered, especially in the weeks before active testing and surveillance became available in the United States. Moreover, healthcare workers who work in the “frontline” or directly with patients infected with SARS-COVID-2, are at higher risk of infection.

Another important aspect of finding detectable IgG antibody titers is the use of plasma from recovered patients with COVID-19 in a similar fashion as it has previously been used to treat outbreaks other potentially lethal infectious diseases such as SARS, Ebola, diphtheria, measles, etc. before a vaccine was available. On March 24, 2020, the FDA announced a pathway to facilitate access to COVID-19 convalescent plasma for use in patients with serious or immediately life-threatening COVID-19 infections. This therapy relies on circulating serum antibodies that are able to, either prevent infection via blocking interaction of the virus with the host cell receptor, or that can potentiate antibody-dependent cell-mediated cytotoxicity (ADCC).

Hypothesis: A proportion of healthcare workers have previously been exposed and recovered from SARS-COVID-2. Detectable IgG antibodies against SARS-COVID-2 would indicate evidence of past infection. Moreover, the development of IgM or IgG antibodies during the study period would indicate exposure to the virus.

Inclusion criteria:

- All healthcare workers participating in the chemoprophylaxis trial will be offered participation.

Accordingly, the Biotechnology Center within the Baylor Institute for Immunology Research has initiated a viral serology study to collect serum/plasma samples from those participating in the study that also agree to have blood samples obtained. The donors that have the highest titers of

antibodies directed to SARS-COV-2 proteins will have the highest potential for eliciting potent therapeutic benefit.

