12.2.1. Primary Analysis of Efficacy

All subjects who received at least one dose of study medication, will be used as the primary population for assessment of efficacy. The proportion of people whose NP sample becomes positive at least once during the trial will be compared between the study groups using Chi square or Fisher exact test. Survival analysis will be utilized to estimate the potential effects of hydroxychloroquine on COVID-19 free survival times. We will apply generalized linear mixed models to compare the positive conversion rate of COVID-19 between the study arms while controlling for other confounding factors. AIC and BIC criteria will be used to choose an appropriate covariance structure between the measurements collected at consecutive visits. An

interaction effect between time and study group will be added to the model to evaluate whether the relative risk of a positive conversion changes from visit to visit.

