5.1. Intention-to-treat (ITT)

- All subjects who received the study drug
- All subjects who participated in at least one post-baseline assessment

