5.2. Per Protocol (PP)

All randomised study subjects completing the whole study period (complete cases)

6. Analyses

All statistical analyses and data summaries will be performed using SAS® (Version 9.1 or higher) or other validated software. The SAP will serve as the final arbiter of all statistical analyses. Data will be summarized overall using descriptive statistics. Continuous data will be summarized with number of subjects (n), mean, median, minimum, maximum, relevant quartiles, standard deviation, coefficient of variation, and geometric mean (where applicable). Categorical data will be summarized using frequency counts and percentages. Chi Square or Fisher exact test will be used for comparing binary outcomes between treatment and control groups. Continuous variables will be compared between the study groups by means of two sample T test or Wilcoxon-rank-sum test.

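### Positive conversion has no at-risk rule: the status of a positive pre-dose Day 1 swab is undefined, and the adjusted mixed model is not stated to end at the first positive swab

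*Protocol*

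**What the plan says.** **Endpoint wording.** The endpoint (Protocol 6.2.1, SAP 4.1) is the rate of positive conversion on weekly NP swabs. The synopsis analyses "The proportion of individuals who tested positive at least once during the study period". Protocol 12.2.1 and SAP 6.1 analyse "The proportion of people whose NP sample becomes positive at least once during the trial". On precedence, SAP section 6 states: "The SAP will serve as the final arbiter of all statistical analyses".

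**Day 1 swab.** Table 3 (Protocol 7.5) marks NP sampling at Day 1 and at every visit from Day 7 to Day 49. Its footnote b reads: "On Day 1, all procedures should be performed before study drug administration". Controls follow the same swab schedule.

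**Entry.** Protocol 8.1 asks for exposure and for participants to be "Afebrile with no constitutional symptoms". Neither 8.1 nor 8.2 contains a swab condition. Protocol 9.8.17 expects infection without symptoms: "Given a high number of asymptomatic or minimally symptomatic infections".

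**Populations.** The synopsis schema describes "the study population being those who either received hydroxychloroquine or entered the observational registry". Protocol 12.2.1 and SAP 6.1 take everyone with at least one dose. SAP 5.1 has two bullets, receipt of study drug and "All subjects who participated in at least one post-baseline assessment", and does not say whether both must be met. None of these mentions the Day 1 result.

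**Adjusted model and missing data.** SAP 6.1 applies a generalized linear mixed model, with a covariance structure across visits, a group-by-time interaction and control for confounders. SAP 7 uses multiple imputation when more than 5% of data are missing, and linear mixed models otherwise.

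**After a positive test.** Protocol 8.4.1 lists a positive test as a reason to stop drug and keeps the participant in all visits and assessments where possible. Protocol 9.1.5 stops study treatment and procedures.

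**The concern.** **(a) Primary test.** Taken literally, the synopsis counts a Day 1 positive as an outcome. The word *becomes* in 12.2.1 and SAP 6.1 points the other way but supplies no rule. Even on that reading, nothing says whether a Day 1 positive leaves the denominator or stays in it as a non-event, or whether a Day 7 positive from an infection already present on Day 1 counts. If such infections are counted and equally common in both arms, the risk ratio moves toward 1. Participants choose their own group (Protocol 7.3), so prevalence may differ and the bias can then go either way. The study is open label, so a choice left unwritten could be made with results in view.

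**(b) Adjusted model.** This is the only comparison said to control for confounding in self-selected groups. Its interaction sentence suggests first conversion; its covariance sentence suggests all repeated results. If swabs continue after a positive (8.4.1), one infection can contribute several positive records. If they stop (9.1.5), the absent swabs could be treated as missing and imputed, because SAP 7 does not exempt them. SAP 7's other branch, linear mixed models, does not suit a yes/no result, although it may not be reached with 15% loss assumed.

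**Working it through.** **Inputs from the documents** (Protocol 12.1, SAP 2.1): 180 per arm, 15% loss, one-sided 0.05, 30% positive on hydroxychloroquine, 40% relative reduction, Pearson chi-square. Evaluable per arm: 180 × 0.85 = 153. The synopsis threshold of p < 0.05 does not state sidedness, so both versions are shown where they matter.

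**The plan's own figure.** As worded, the control rate is 0.30/0.60 = 50%. Eighty percent power then needs 74 evaluable per arm, and 74/0.85 gives 88, or 176 in total. This is not 360; power at 153 per arm is 97.5%. Reading 30% as the control rate (18% vs 30%) needs 156 per arm. Then 156/0.85 gives 184 (368 in total), while 156 × 1.15 gives 180 (exactly 360); power at 153 is 79.4%. Both readings are carried below. The second is my reinterpretation.

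**Assumption.** The Day 1 prevalence *b* is not given, so ranges are used.

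**Equal prevalence, Day 1 positives counted.** Observed risk = b + (1 − b)p. Power is from the pooled two-proportion z formula.

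| Rates | b | Observed risks | RR | Power, one-sided 0.05 | Power, two-sided 0.05 |
|---|---|---|---|---|---|
| 30% vs 50% | 0 | .300 / .500 | .600 | 97.5% | 95.0% |
| | 2% | .314 / .510 | .616 | 97.0% | 94.0% |
| | 5% | .335 / .525 | .638 | 95.9% | 92.3% |
| | 10% | .370 / .550 | .673 | 93.8% | 88.9% |
| 18% vs 30% | 0 | .180 / .300 | .600 | 79.4% | 69.2% |
| | 2% | .196 / .314 | .625 | 76.5% | 65.7% |
| | 5% | .221 / .335 | .660 | 72.1% | 60.6% |
| | 10% | .262 / .370 | .708 | 65.2% | 52.9% |

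If they are excluded, n = 153(1 − b) and the RR stays 0.60. One-sided power at 18% vs 30% is then 78.7%, 77.6% and 75.6% for b = 2%, 5% and 10%.

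**Unequal prevalence, no drug effect, Day 1 positives counted.**

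| Incident risk | Day 1: control / drug | RR | Result |
|---|---|---|---|
| 30% | 8% / 3% | .321/.356 = .902 | False benefit 15.9% (nominal 5% one-sided); 9.4% (nominal 2.5% per side) |
| 30% | 6% / 4% | .328/.342 = .959 | False benefit 8.3%; 4.4% |
| 30% | 3% / 8% | .356/.321 = 1.109 | False harm 9.4% (nominal 2.5%) |
| 50% | 8% / 3% | .515/.540 = .954 | False benefit 11.4%; 6.4% |

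A binomial simulation (400,000 runs) of the uncorrected chi-square agrees: 16.1% and 9.4% in the first row, 8.5% and 4.5% in the second, 11.1% and 6.0% in the last. Restricting to Day 1 negatives (148 drug, 141 control) with equal incident risk returns 5.0% and 2.5%. Keeping Day 1 positives in the denominator as non-events also biases: at 8% / 3% the RR is 0.97/0.92 = 1.05.

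**Against the synopsis's smallest important reduction of 5%.** With no drug effect and 3% positive in the drug arm, an RR of 0.95 arises as follows:
- 30% risk: .321/.95 = .3379, and (.3379 − .30)/.70 = 5.4% in controls, a gap of 2.4 points.
- 50% risk: .515/.95 = .5421, and (.5421 − .50)/.50 = 8.4% in controls, a gap of 5.4 points.

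Read as 5 percentage points, the gap needed is .05/(1 − p), about 7 and 10 points.

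**Part (b).** If procedures stop at the first positive, the absent swabs as a share of the seven follow-up swabs are p × 3/7 when conversions are spread evenly: 7.7%, 12.9% and 21.4% at 18%, 30% and 50% conversion. With a constant weekly hazard they are 8.0%, 13.7% and 24.2%. All exceed SAP 7's 5% trigger. If swabs continue (18% vs 30%, 1 to 4 positive weeks per infection assumed), the per-swab RR is 0.592 to 0.600, against 0.563 when records end at the first positive. With equal 30% incidence but 2 positive weeks on drug and 3 on control (assumed), it is 0.715 despite no effect on conversion.

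**The case against.** The governing text leans one way. The endpoint is called conversion throughout, 12.2.1 and SAP 6.1 say *becomes*, the SAP prevails, and SAP section 2 lists visits only from Day 7. A person positive on Day 1 does not convert. Only the synopsis says otherwise. This stands as a reading, but it leaves the denominator and window unstated, and SAP 5.1's post-baseline bullet does not exclude Day 1 positives.

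The sizes rest on assumed prevalence. At the rates as worded, 5% Day 1 positives cost under 2 points of one-sided power. The larger loss needs the 18% vs 30% reading. Both points stand.

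The false-benefit figures need an assumed imbalance. Group choice follows eligibility and no swab is scheduled before Day 1, so choice cannot normally follow the result. Differing prior exposure could still create a gap, but that is self-selection, which also affects incident infection and which this fix does not remove. That also stands.

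Part (b) has limited reach. With equal duration of positivity the estimate moves little, the larger distortion needs an assumed difference between arms, and imputation of later swabs is a possibility rather than a stated plan. Swabs after the first positive do not affect the chi-square or Fisher test or time to first positive.

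**Conclusion.** The concern holds and should be fixed; confidence is medium because the size cannot be fixed from the documents. It is an omission, not an arithmetic error. Following the synopsis rule with the all-dosed population puts infections the drug cannot prevent into the primary comparison. Dilution alone is modest at 30% vs 50% and matters more at 18% vs 30%. The more serious risk is imbalance between self-chosen groups: a 2.4-point Day 1 gap at 30% risk is enough, with no drug effect, to produce the plan's smallest important reduction if that is read as relative. Part (b) is secondary and concerns only the adjusted comparison, whose outcome and records are undefined.

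**What to change.** 1. Define conversion as the first positive NP swab after Day 1 among participants whose Day 1 swab was negative. Use the same sentence in the synopsis, Protocol 12.2.1 and SAP 6.1.
2. State in SAP 5.1 how its two bullets combine, and align the synopsis's intent-to-treat sentence with the new at-risk set. Report Day 1 positives by group and keep them in the safety analysis.
3. End each participant's records in the adjusted visit-level model at the first positive or last swab. A discrete-time hazard model with the confounders and group-by-visit is one suitable form.
4. In SAP 7, state that swabs after a first positive are neither missing nor imputed, and replace linear mixed models with a method for a binary outcome.
5. Reconcile Protocol 8.4.1 and 9.1.5 on whether visits and procedures continue after a positive test.

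**Cost.** Wording only, since both groups already have the Day 1 swab. A few participants leave the efficacy denominator. Infections still incubating on Day 1 and other confounding from self-selection remain. With 5% Day 1 positives, one-sided 0.05 and 80% power, enrolment needed per arm at 30% vs 50% is 92 if they are excluded and 98 if counted (88 with none), within the planned 180. At 18% vs 30% it is about 194 if excluded (184/0.95) and 224 if counted (190/0.85), against 184 with none.
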